In exploratory analyses, we will examine whether increases in implementation of FAPB from baseline to follow-up are associated with rates of sexual victimization. For these analyses we collapse our follow-up data into dichotomous variable indicating whether sexual victimization occurred. Using a two-level HLM (individuals nested within dyads), this dichotomous outcome will be regressed on the intercepts and slopes from our growth models of FAPBs (described above). Steeper increases in FAPBs are expected to be associated with lower likelihood of sexual victimization at follow-up controlling for baseline levels of sexual victimization. Odds ratio will be used to describe the effect size. Data from stakeholder and exit interviews will be analyzed using qualitative data analytic techniques.

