## 20.0 Risks to Subjects

### 20.1 List the reasonably foreseeable risks, discomforts, hazards, or inconveniences to the subjects related to their participation in the research.

**Response:** Risks posed to participants in the present study are minimal. Evidence shows that assessments of sexual assault and related experiences may be conducted without serious deleterious psychological effects. Some participants may experience minor emotional discomfort or embarrassment in responding to questions pertaining to potentially sensitive topics such sex or sexual assault, or even substance use. This could occur during completion of self-report assessments, or during individual interviews. However, such discomfort is relatively rare, and is almost always mild and transient. Our labs have been conducting both in-person and online assessments of these phenomena for more than a decade and are well equipped to manage participant needs in the event that distress occurs (see below).

As this dyad-based intervention focuses on motivating a sense of agency for action, through enhancement of personal responsibility and relationship between friends, another potential risk pertains to inadvertent, iatrogenic effects of the intervention. For example, in cases where sexual victimization occurs to one of the dyad members – or even if it doesn't- the other member of the dyad may believe that somehow she is to blame. We plan to assess such effects carefully, with an eye toward both (1) modification of the intervention to decrease such iatrogenic effects, and also (2) ensuring the wellness of the participants enrolled in our study. Efforts to address the first of these issues (future intervention modification) are described in the body of the proposal. To address specific participant wellness concerns, here we outline several steps that we will take in the "Adequacy of Protection Against Risk" section, below.

Lastly, because our study focuses on high-risk (i.e., heavy drinking) women, it is possible and perhaps even likely that women will experience some kind of event that falls along the spectrum of assault behaviors during the course of follow-up. Though this assault would not be as a result of the intervention itself, it is a risk that our participants could incur during the period of follow-up and as such, is something that we have planned to address in our procedures. These procedures are described below.

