*Assessment and Management of Adverse Events.* Our procedures for managing adverse events are informed by the collective experience of our team in conducting research with women at risk for assault and other adverse, alcohol-related outcomes, including [name] training as a Clinical Psychologist and her experience as the Director of the Clinical Psychology program, including the Psychological Services Clinic. All study staff, including interventionists and research assistants, will be trained to identify serious adverse events that may be subject to mandatory reporting guidelines. Related to this, staff also will be trained to identify any events that, though falling short of mandatory reporting requirements, may nonetheless be warranting immediate clinical attention (e.g., recent sexual assault or assault-related distress). Any evidence that a participant may be in immediate and identifiable danger, or is experiencing other significant and acute distress (e.g., recent assault) will trigger an “emergency procedures” protocol. In these cases, the PI ([name]) will be notified by telephone and text of such an event. In cases where this “triggering” occurs via online assessment, [name] will make immediate phone contact with the participant to further evaluate safety and other concerns. In cases where the triggering takes place during in-person assessments, [name] will be contacted and will speak with the participant either by phone (if [name] is off-site) or in person to provide further assessment and to formulate an action plan to ensure the participants safety and wellbeing. In the unlikely event that [name] cannot be reached within the hour, either the Campus Psychological Services Center (PSC) or if outside of business hours, Campus Security will be contacted. In cases where the threat is determined not to be imminent, [name] will work with the participants to connect them to services at either the PSC or the university-based Counseling Center. At both of these facilities, students may receive either free or reduced rate services. Drs. [name], [name], and [name] have close ties to these facilities. This will ensure a seamless pathway of care.

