*Outcome analyses.* The primary goals of Aim 3 are to evaluate whether (1) FMI increases readiness and reduces perceived barriers to intervene, and increases alcohol knowledge and strategies post-intervention and over the follow-up (2) FMI increases the implementation of friend-based assault-protective behaviors (FAPB) in our 3-month follow-up, and (3) changes in readiness and perceived barriers for protective behaviors, and alcohol knowledge and strategies are associated with implementation of FAPDs at 3-month follow-up (potential mechanisms). We will also examine if quality of the dyad relationship changes as a function of the intervention. Increases or decreases in relationship quality as a function of the intervention would suggest either a positive impact on dyadic relationships or iatrogenic effects of the intervention, respectively. Whether increases in implementation of behavioral strategies are associated with reduced rates of sexual victimization will also be examined. Examination of sexual victimization is exploratory, as victimization rates are expected to be relatively low over the short follow-up period (i.e., approx. 30% across 3 months; Parks et al., 2008). In secondary analyses, we will also consider alcohol use as an outcome variable to examine potential intervention effects on drinking. Given the pilot nature of the R34 mechanism and the smaller sample size, we will focus analysis on effect sizes and whether effects are in the proposed direction. Effect size estimates can be unreliable in small pilot studies (Kraemer et al., 2006); thus, we will report effect sizes ranges (95% confidence bands).

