A prominent feature of our design is that individuals are nested within dyads, and this necessitates a data analytic approach that can accommodate nested data structures. Hence, our Aim 3 analyses are built around hierarchical linear models (HLMs). First, we will evaluate group differences on variables from our first post-intervention assessment (i.e. perceived barriers, readiness, alcohol knowledge and strategies, and implementation of FAPBs) using a two level model (individuals nested within dyads). Treatment will be dummy coded (FMI vs. waitlist control group) and included as a level two covariate. Second, we will utilize all data from our three month follow-ups and repeat these analyses using a three-level model (6 repeated measures nested within individuals, and individuals nested within dyads). In these models treatment will be included as a level three covariate. We will use  $\beta$  to describe effect sizes (Cohen, 1988; Selya et al., 2012).

Our burst design provides a rich opportunity to examine whether changes in target constructs of interest (e.g., barriers, skills, alcohol knowledge and strategies) are associated with implementation of FAPBs. For these analyses we will combine the post-intervention data from our FMI and WLC groups after the latter has completed the intervention and follow-up assessments. Combining groups will increase our sample size and provide more stable estimates of effect sizes. For these analyses we will include reports of past week protective behavioral strategies just prior to the intervention and weekly aggregates of variables of interest from our three-month follow-up yielding 7 repeated measures nested within individuals and individuals nested within dyads. Time will be included as a level-1 covariate, and we will

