examine change in readiness, perceived barriers, alcohol knowledge and strategies, and implementation of FAPBs. Effect sizes characterizing change will be computed in two ways: 1). Computing a difference score using baseline and the first follow-up divided by the standard deviation of the difference score, and 2). A difference score using baseline and the last assessment of the follow-up divided by the standard deviation of the difference score (Gibbons et al., 1993; Morris & DeShon, 2002). Individual level intercepts and slopes will be output from these models and this will allow us to examine correlations between slopes and intercepts. We expect that reductions in perceived barriers (better self-efficacy, fewer interpersonal concerns), and increases in readiness will be positively related to implementation of FAPBs. Our models will also allow us to include individual characteristics (e.g. assault history, drinking history, relationship, responsibility) to examine their association with change in perceived barriers, skill implementation, etc. (e.g., prior history of sexual assault is related to more or less change in variables our intervention is expected to impact).

In exploratory analyses, we will examine whether increases in implementation of FAPB from baseline to follow-up are associated with rates of sexual victimization. For these analyses we collapse our follow-up data into dichotomous variable indicating whether sexual victimization occurred. Using a two-level HLM (individuals nested within dyads), this dichotomous outcome will be regressed on the intercepts and slopes of FAPBs (described above). Steeper increases in FAPBs are expected to be associated with lower likelihood of sexual victimization at follow-up controlling for baseline levels of sexual victimization. Odds ratio will be used to describe the effect size. Data from stakeholder and exit interviews will be analyzed using qualitative data analytic techniques.

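### The exploratory victimization odds ratio uses protective-behavior slopes that include reports made after the event, so its direction cannot be read as protective or harmful

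*Combined protocol and SAP*

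**What the plan says.** The outcome discards timing: "we collapse our follow-up data into dichotomous variable indicating whether sexual victimization occurred" (Statistical Analysis Plan, exploratory analyses). The predictors are each woman's FAPB intercept and slope: "this dichotomous outcome will be regressed on the intercepts and slopes of FAPBs (described above". Protocol section 16.1, Aim 3, specifies the same: "this dichotomous outcome will be regressed on the intercepts and slopes from our growth models of FAPBs".

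The slopes come from the change models in the SAP's Outcome analyses. These combine one report made just before the intervention with "weekly aggregates of variables of interest from our three-month follow-up yielding 7 repeated measures", so six of the seven waves lie in the outcome window.

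The only stated adjustment is baseline victimization. Nothing lags FAPB, restricts it to reports before the event, or ends a woman's follow-up at her event. The SAP attaches a direction: "Steeper increases in FAPBs are expected to be associated with lower likelihood of sexual victimization at follow-up". It labels the analysis exploratory and expects a rate of "approx. 30% across 3 months".

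**The concern.** A slope fitted to the whole follow-up contains behavior that came after the event as well as before it. For a woman victimized early, most of the slope is later behavior. If an assault changes what she or her friend does, or how often they go out, the slope is partly a consequence of the outcome, and adjusting for baseline victimization does not restore the order.

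The documents give reasons why FAPB might change but do not say that it does, or in which direction. Section 20.1 foresees that after victimization "the other member of the dyad may believe that somehow she is to blame". Section 20.2 says that evidence of a participant "experiencing other significant and acute distress (e.g., recent assault) will trigger an" emergency protocol, which brings staff contact. Section 10.3 ties the bi-weekly report to outings with the target friend, which may become fewer.

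This is the only analysis the SAP spells out with victimization as the outcome, and the SAP says it will concentrate on the size and direction of effects. If FAPB falls after an assault, the artefact resembles the expected result. If it rises, a real protective association can be hidden or reversed.

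**Working it through.** The documents give no odds ratio, power or precision for this analysis, so there is no stated figure to reproduce.

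**Inputs from the documents.** Seven waves, six of them in follow-up (SAP, Outcome analyses). 30% victimized over 3 months (same section). Women: 96 (48 dyads, Stage 3), 92 (timeline, 11.3) or 88 (16.2).
**Assumed.** An even hazard over six two-week intervals, and the size of any FAPB shift after an event.

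**1. Events.** 0.30 × 88 = 26.4; 0.30 × 96 = 28.8. About 26 to 29.

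**2. Overlap.** Hazard per interval h = 1 − 0.7^(1/6) = 0.0577. Among victimized women, P(first recorded at assessment k) = (1 − h)^(k−1) × h / 0.30, which is 0.192, 0.181, 0.171, 0.161, 0.152, 0.143 for k = 1 to 6. Later reports number 6 − k.
- Mean: 5(0.192) + 4(0.181) + 3(0.171) + 2(0.161) + 1(0.152) = 2.67 of 6.
- At least one later report: 1 − 0.143 = 86%.
- At least three (k ≤ 3): 54%.

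**3. Effect on a fitted line.** Waves 0 to 6, centred, have sum of squares 28. A one-unit shift after assessment k changes the least-squares slope by 5/28, 6/28, 6/28, 5/28, 3/28 and 0 for k = 1 to 6. Weighted by step 2, the mean is 0.155 per wave. A shift of 0.5 SD moves victimized women's slopes by about 0.077 on average, and the other women's not at all.

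**4. Illustrative odds ratio per SD of slope when FAPB has no effect on risk.** All inputs are assumed, and every victimized woman receives the same lasting shift.
- A: 48 dyads, empirical-Bayes slopes, SD of one report 1, true slope SD 0.10 per wave, assault history as covariate, dyad-clustered errors.
- B: a separate simulation with least-squares slopes and no history covariate; rates at 88 women.
- C: as A, with slope SD 0.20 (more reliable slopes).

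| Shift after event | A: OR (interval excludes 1) | B: OR (p < 0.05) | C: OR |
|---|---|---|---|
| −0.5 SD | 0.59 (50%) | 0.52 (63%) | 0.69 |
| −0.2 SD | 0.81 (13%) | 0.77 (15%) | 0.85 |
| 0 | 1.00 (6%) | 1.00 (4%) | 0.98 |
| +0.2 SD | 1.22 (13%) | 1.30 (16%) | 1.12 |
| +0.5 SD | 1.69 (50%) | 1.93 (65%) | 1.38 |

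In B, a model of first event on FAPB change from baseline to the previous report, with baseline level included, gave 1.00 at every shift (4.6% false positives). That is largely by construction: women leave at their first event, and no confounding was simulated.

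**5. Against sampling error.** The standard error of the log odds ratio per SD of slope is at least about 1/√(96 × 0.3 × 0.7) = 0.22, a 95% interval of roughly ×/÷ 1.55. A bias from a 0.2 SD shift lies well inside that interval.

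**6. Could a time-ordered model replace the plan?** Take no FAPB effect and no shift, with risk depending only on a woman's stable FAPB level (assumed odds ratio 1.35 or 1.65 per SD). A model using the previous FAPB level gave 1.24 or 1.37, with 21% or 37% false positives. The planned slope odds ratio stayed at 1.01 or 0.99 (5 to 6%), because the intercept absorbs the stable level. Adding baseline FAPB to the time-ordered model lowered 1.37 only to about 1.21. Where risk depends only on the whole-period slope (assumed odds ratio 0.5 per SD, no shift), the planned model detected it in 53% of runs and the lagged-level model in 12%. Each model fails where the other does better.

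**The case against.** The other side has a good case. The analysis is exploratory, worded as an association, in a pilot that reports effect sizes with intervals. With no shift there is no bias, and no passage says that FAPB changes after an event. Section 10.3 defines victimization from unwanted attention to completed rape, with milder events more frequent, so a lasting 0.5 SD shift after any event is a strong assumption. The SAP's question concerns increases from baseline to follow-up, which the slope addresses directly.

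All of that stands, and it limits severity. It does not remove the point: the SAP states an expected direction, direction is what this overlap can distort, and a confidence interval does not reveal it.

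A reader might infer that the planned odds ratio will look falsely protective. The documents do not support that, since they fix neither the existence nor the sign of a shift. A reader might also infer that a lagged model should take the plan's place. Step 6 argues against this: stable differences between women, such as how often a pair goes out, can distort the lagged model while leaving the planned slope term largely untouched, provided they are unrelated to slope.

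**Conclusion.** The overlap is certain from the text: predictor and outcome share one follow-up window, and nothing separates FAPB before the event from FAPB after it. Its extent, about 2.7 of 6 reports per victimized woman, rests on the plan's 30% and an assumed even hazard. Bias is conditional on FAPB changing after an event, and its direction is undetermined. The sizes in step 4 show what assumed shifts would do; they are not predictions.

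Severity is minor to moderate. The randomized comparisons do not use these slopes, so it would be wrong to infer that the trial's main results are affected. What cannot stand is reading this odds ratio as evidence that increases in FAPB lower victimization.

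**What to change.** 1. **Keep the planned slope regression and label it.** State that its slopes include FAPB reported after the event, report it as a concurrent association, and do not treat its direction as evidence of protection.
2. **Add a time-ordered sensitivity analysis, not a replacement.** Model first victimization in each bi-weekly interval on FAPB change from baseline to the previous assessment, with baseline FAPB level, interval indicators, dyad clustering and the planned adjustment for baseline victimization. Read a direction only if both analyses agree.
3. **Settle the data definitions first.** Section 10.3 asks about outings since the last assessment but about assault in the prior week; reconcile the two. State whether an event to the friend counts as the woman's outcome, since assault items are coded for either. State which FAPB measure is used (one is collected only for drinking occasions) and what happens when the previous report is missing (the retention bonus needs only 4 of 6).

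**Cost.** SAP wording and modest programming; section 10.3 already collects FAPB bi-weekly and codes assault by occasion.

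**Limits to state in the SAP.**
- There are about 26 to 29 events. In the first interval the change from baseline is zero by definition, so about 19% of events say nothing about change, leaving roughly 21 to 23 (26.4 and 28.8 × 0.808).
- With prior-week recall only, the total falls to about 88 or 96 × (1 − 0.7^0.5) = 14 to 16.
- The added model has less power for an effect carried by the whole-period slope.
- It remains open to confounding by stable FAPB level and outing frequency, which baseline FAPB removes only in part.

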#### **Bi-Weekly Follow-Up Assessment**

**Overview:** Bi-weekly, participants will report on any occasion since the last assessment that the participant was out with the target friend in a social setting. For each such occasion, we will collect information about the context of these occasions (i.e., bar, party, out to dinner), whether there was alcohol, who was present, and whether there was an opportunity for intervention.

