#### **Friend-Based Assault Prevention Behavior Skills (FAPB)**

*Peer-Directed Bystander Behaviors for Sexual Assault Prevention (Baseline, bi-weekly).* We will use the 49-item Bystander Behaviors Scale for Friends (Banyard et al., 2014), which includes 4 subscales (1) the identification of sexual assault risk situations, (2) accessing resources, (3) planning ahead for risk situations, and (4) safety behaviors in risk settings. This measure will be adapted to include a broader

range of protective behaviors based on findings at Stage 1, and some of the items that refer to intimate partner violence will need to be reworded to assess sexual violence. Participants will complete this measure with respect to their target friend (i.e., did they do this for their friend) and also for themselves (i.e., did their friend do this for them?).

*Sexual Assault-Related Protective Behaviors (baseline, bi-weekly for all drinking occasions).* A measure developed by Armstrong et al., the Women's Peer-Directed Protective Strategy questionnaire (WPPS) will be used to evaluate assault-specific protective behaviors. This 24 item measure includes items such as, "I try to be aware and monitor where my friends are at all times," and, "I watch out for my friends in an attempt to keep them away from (risk) situations". Participants will complete this measure for their target friend (i.e., did they do this for their friend?) and also for themselves (i.e., did their friend do this for them?). Participants will be asked to rate frequency and how effective they perceived each behavior to be. They also will rate how they felt about it when they or their friend engaged in the behavior or did not engage in the behavior (when there was an opportunity) using a brief checklist of positive and negative feelings (e.g., good, relieved, safe, guilty, angry, scared). This will be based on information from qualitative participant interviews at earlier stages.

We also will assess whether the intervention resulted in unanticipated or adverse consequences, such as placing undue stress on a member of the dyad, or straining the friendship.

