#### Assault and Drinking Outcomes

*Alcohol Consumption (bi-weekly, all drinking occasions).* Using a grid-based average assessment measure based in the Daily Drinking Questionnaire (Collins et al., 1985), participants will report on alcohol consumption, on occasions when they were out with the target friend. See above for detailed description.

*Sexual assault (bi-weekly).* This intervention is designed to target risk for a full range of non-consensual sexual experiences, from unwanted sexual attention, to completed rape. Because lower-severity events are more frequent and may signify risk for higher severity events, it may be in lower-severity situations where there is greatest opportunity for intervention. Following Kelley-Baker (2008) for assessing assault-events for particular occasions, we will use the Revised SES to assess each social occasion with the target friend in the prior week. Each item will be coded 1(yes) or 0 (no), based on whether it happened to the woman/friend on each occasion that the pair socialized together.

*Alcohol-Related Protective Behaviors (baseline, bi-weekly).* Because one strategy women may use to decrease assault risk is to limit their own and friend's alcohol consumption, we will administer the Protective Behaviors Strategy Survey (PBSS; Martens et al., 2005).

Treatment Evaluation. (Used in Stages 2, 3; from Borsari et al., 2007)

End of Session Questionnaire. Completed at the end of the intervention session, this 6-item measure evaluates the participant's perceptions of the personal relevance of and engagement in the session. Participants also will complete a 1page survey that asks about their experiences in the session.

End of Treatment Questionnaire. This 48-item measure assesses participant perceptions of the helpfulness of each treatment component on a scale from -3 (*greatly harmful*) to +3 (*greatly helpful*). Participants will also be asked to elaborate on their perceptions of what was helpful and/or harmful (i.e., iatrogenic effects).

Therapist Assessment. (Used in Stages 2, 3)

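### The exploratory victimisation regression ignores the number of outings, so its odds ratio is biased upward if FAPBs are scored as totals or any-use per period

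*Combined protocol and SAP*

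**What the plan says.** **Outcome.** Protocol section 10.3 (Assault and Drinking Outcomes) codes each victimisation item yes or no, "based on whether it happened to the woman/friend on each occasion that the pair socialized together". The SAP then makes one variable per woman: "For these analyses we collapse our follow-up data into dichotomous variable indicating whether sexual victimization occurred".

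**Model.** In a two-level model, "this dichotomous outcome will be regressed on the intercepts and slopes of FAPBs (described above". The only adjustment named is baseline victimisation, which section 10.3 measures as lifetime history. The SAP expects steeper FAPB increases to go with less victimisation.

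**FAPB score.** One instrument, the WPPS, is completed "bi-weekly for all drinking occasions". On scaling, section 10.3 says: "Participants will be asked to rate frequency and how effective they perceived each behavior to be". The other, the 49-item Bystander Behaviors Scale, is bi-weekly and has subscales for planning ahead and accessing resources. The SAP enters these measures as weekly aggregates at 7 time points and does not say whether an aggregate is a sum, an any-use indicator or a mean.

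**Outings.** Section 10.3 collects them: "Bi-weekly, participants will report on any occasion since the last assessment that the participant was out with the target friend in a social setting". It also records "whether there was an opportunity for intervention". Neither appears in any model in protocol section 16.1 or the SAP. The growth models have time and, optionally, assault history, drinking history, relationship and responsibility. Other baseline covariates enter only if the arms differ.

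**The concern.** A woman who goes out with her friend more often has more occasions on which victimisation can be recorded. If her FAPB score also grows with the number of occasions, the two are positively associated even when FAPBs do nothing. That is the reverse of the hypothesis, so a real protective association could be hidden or a spurious harmful one could appear. The SAP says that, given the small sample, it will judge results by effect size and by whether effects lie in the proposed direction. Direction is what this omission can distort. The study also looks for iatrogenic effects, so a false signal of harm could mislead the next stage of development.

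**Working it through.** **Inputs from the documents.** Expected victimisation is about 30% over 3 months (SAP, Outcome analyses). Pairs must go out together at least once a week, with no upper limit (section 6.1), which is 12 outings in 12 weeks. Stage 3 has 48 dyads, or 96 women (section 4). The power section (16.2) gives 88. The 30% comes from a cited study and cannot be reproduced from the documents, so it serves as a calibration value.

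**Step 1: outcome and outings.** With constant risk p per outing, P(any) = 1 − (1 − p)^n. If 12 outings give 30%, then p = 1 − 0.70^(1/12) = 0.029, and:

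- 18 outings: 1 − 0.70^1.5 = 41%
- 24 outings: 1 − 0.70^2 = 51%
- 36 outings: 1 − 0.70^3 = 66%

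This part needs no assumption about FAPBs.

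**Step 2: FAPB score and outings.** A sum over outings, or an item scored as done at all in the period, rises with n. A mean per outing does not. The SAP wording allows all three.

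**Step 3: the planned regression with no FAPB effect.** Simulated FAPBs at 7 time points gave each woman a least-squares intercept and slope. Any victimisation, set to 30% overall, was regressed on both by logistic regression. Assumptions not in the documents: a mean of 3 outings per two weeks, between-dyad coefficient of variation (CV) 0.3 or 0.5, individual trends in outings with SD 0 or 0.4 on the log scale, and 0.5 to 0.75 FAPB acts per outing. Baseline victimisation was not simulated. Large-sample odds ratios per SD of FAPB slope:

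| FAPB scoring and outings | As planned | With log outings added |
|---|---|---|
| Total, CV 0.3, stable | 1.29 | 1.01 |
| Total, CV 0.5, stable | 1.37 | 1.01 |
| Total, CV 0.5, individual trends | 1.51 | 1.02 to 1.03 |
| Any-use per period, CV 0.5, individual trends | 1.56 | 1.01 |
| Mean per outing, CV 0.5, individual trends | 1.00 | 1.00 |

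A complementary log-log model with log outings as offset, the form Step 1 implies, gave a relative risk of 1.00 throughout.

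**Step 4: at trial size, total scoring** (1,500 replicates, dyad-clustered standard errors). The slope odds ratio exceeded 1 in 81% to 94% of trials at 96 women and 80% to 93% at 88. It was significantly above 1 in 16% to 37% and 14% to 35%, against a nominal 2.5%. With log outings added, that fell to 2.3% to 2.9%.

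**Step 5: a truly protective behaviour** (total scoring, CV 0.5, individual trends). With a per-outing relative risk of 0.67 per SD of behaviour, the slope odds ratio was 1.21 as planned and 0.69 with log outings.

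**Step 6: a score only partly tied to outings.** A second assumed set used a constant 4 FAPBs per outing, SD of log outings 0.3 to 0.5 and SD of its 12-week change 0.25 to 0.5. It gave 1.58 to 1.74 when the whole score scales with outings (1.54 to 1.66 with dyads below one outing a week removed). This fell to 1.26 to 1.48 when half the score is independent of outings and 1.09 to 1.24 when three quarters is. The documents give no such weights. This set is used for the dilution, not for the level.

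**The case against.** The strongest objection is that the FAPB half of the argument is not in the documents. Planning ahead and accessing resources are not confined to outings. Only the WPPS is tied to occasions, and a frequency rating can be relative (how often when out) and need not rise with outings. Because the WPPS is completed by occasion, a per-occasion mean is a natural reading of the weekly aggregate, and under it the bias disappears. This stands, and it makes the point conditional on a scoring rule that the SAP leaves open.

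The remedy is also not neutral. Follow-up outings occur after the intervention and may respond to it. Conditioning on them changes the question from risk over follow-up to risk per outing and discards any benefit gained by going out less. This stands too, and is why the adjusted model should accompany the planned one and not replace it.

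Finally, the analysis is labelled exploratory, in a pilot whose SAP already warns that effect sizes may be unreliable and promises 95% bands. That limits the consequence. It does not remove it, because a confidence band reflects sampling error and not bias.

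A reader might infer more: that outings drive every FAPB score, that the randomised comparisons are distorted, or that seasonal swings in going out will pass for changes in FAPB use. The documents do not support these. Randomisation balances pre-existing differences in outings on average, and no figure is given for how outings vary over time.

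**Conclusion.** The point holds in conditional form. That the any/none outcome rises with outings follows from its definition, and the absence of outings from every model is plain from the text. Whether this biases the FAPB odds ratio depends on scoring. With totals or any-use per period, a null effect gave about 1.3 to 1.6 per SD of slope. With a score partly independent of outings the bias is smaller, and with a mean per outing it is absent. The direction is firmer than the size, because every outing distribution was assumed. The error rates in Step 4 belong to total scoring under those assumptions and do not predict what this trial will show. Baseline victimisation, as lifetime history, is at most a weak proxy for follow-up exposure and is unlikely to remove the problem.

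**What to change.** In the SAP:

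- Define the aggregate. Score occasion-based FAPBs, such as the WPPS, as a mean per outing with the friend over the occasions for which the instrument was completed.
- Add log number of outings to the victimisation regression and report that model beside the unadjusted one, stating that it estimates risk per outing.
- Count outings over the same occasions for which the victimisation items were recorded. Section 10.3 refers those items to the prior week, while the outing report covers the whole time since the last assessment, so the two windows need to be aligned.
- Report outings and opportunities to intervene descriptively by arm, since the FMI may change them.

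The cost is SAP wording and one extra model, using data already to be collected. Intervals with no outing contribute no FAPB rate, and a rule is needed for a woman with no recorded outing, whose log count is undefined. The adjusted model also removes any effect that works through going out less, which is the reason to keep the unadjusted result in view.
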